### 1.3 Program Phase

The following protocol governs a Phase 1 dose escalation clinical trial.

### 1.4 Time Required for Study Completion

First Patient Treated: Q1 2018

Last Patient Last Visit: Q2 2019

### 1.5 List of Acronyms

ADR	Adverse Drug Reaction
AE	Adverse Event
ALL	Acute Lymphoblastic Leukemia
ALT	Alanine Transaminase
AML	Acute Myeloid Leukemia
aPTT	Activated Partial Thromboplastin Time
AST	Aspartate Aminotransferase
BARDA	Biomedical Advanced Research and Development Authority
BP	Blood Pressure
BUN	Blood Urea Nitrogen
CAT	Calibrated Automated Thrombogram
CBC	Complete Blood Count
CBER	Center for Biologics Evaluation and Research
CCI	Corrected Count Increment
CDC	Center for Disease Control
CFR	Code of Federal Regulations
CNS	Central Nervous System
COR	Contracting Officer's Representative (BARDA)
COX	Cyclooxygenase
CPTP	Clinical Pretest Probability
CRC	Clinical Research Center
CRO	Clinical Research Organization
CRF	Case Report Form
CSTD	Closed System Transfer Device
CTPA	Computed Tomography Pulmonary Angiogram
DIC	Disseminated Intravascular Coagulation
DMC	Data Monitoring Committee
DOT	Department of Transportation

DVT	Deep Vein Thrombosis
EDC	Electronic Data Capture
FDA	Food and Drug Administration
FDP	Fibrin Degradation Products
GVHD	Graft-versus-Host Disease
IND	Investigational New Drug
IUD	Intra-Uterine Device
EKG	Electrocardiogram
GGT	Gamma Glutamyl Transferase
HIPAA	Health Insurance Portability and Accountability Act
hs	High sensitivity
IATA	International Air Transport Association
ICF	Informed Consent Form
ICH	International Conference on Harmonisation
ICSI	Institute for Clinical Systems Improvement
INR	International Normalized Ratio
IRB	Institutional Review Board
IU	International Unit
IV	Intravenous
LDH	Lactate Dehydrogenase
MI	Myocardial Infarction
NCI	National Cancer Institute
NHSN	National Healthcare Safety Network
NIH	National Institutes of Health
NZWR	New Zealand White Rabbit
OHRP	Office for Human Research Protections
PE	Pulmonary Embolism
PEF	Peak Expiratory Flow
PERC	Pulmonary Embolism Rule-out Criteria
PF	Prothrombin Fragment
PI	Principal Investigator
Plt	Platelet
PT	Prothrombin Time
RBC	Red Blood Cell
RR	Respiration Rate
SADR	Serious Adverse Drug Reaction
SAE	Serious Adverse Event

SOP	Standard Operating Procedure
TAT	Thrombin Antithrombin
TEAE	Treatment Emergent Adverse Event
TEG	Thromboelastography
TGA	Thrombin Generation Assay
TIA	Transient Ischemic Attack
TGPU	Thrombin Generation Potency Units
USP	United States Pharmacopeia
VTE	Venous Thromboembolism
WFI	Water for Injection
WHO	World Health Organization

## 1.6 Background

Traumatic injury and massive uncontrollable hemorrhage are major public health problems in the United States. Despite rapid, significant, advances in medicine and technology, hemorrhage treatment has in many ways lagged behind other blood product therapies such as coagulation factors and plasma proteins. A systemic hemostatic agent has the potential to fill unmet medical needs in non-compressible bleeding such as internal hemorrhage or diffuse vascular bleeding. Thrombosomes® treatment, if proven safe and effective in human trials, could assist in the management of blood loss associated with trauma, uncontrolled internal bleeding, and/or non- compressible hemorrhage.

In July of 2016, Cellphire completed a clinical study under an exploratory IND in 15 subjects (Thrombosomes n=10 and Control n=5) who received ascending doses of either: 1) Thrombosomes ranging from 1/1,000 to 1/10 of the projected minimum effective dosage (~1.89 x 10^8 Thrombosomes particles per kg or 330 Thrombin Generation Potency Units (TGPU) per kg), or 2) Thrombosomes Control (the mixture of excipients used to stabilize Thrombosomes but without the platelet component). The highest dose achieved was 1.55 x 10^7 particles per kg which has the potential to produce 27 IU of thrombin in-vitro.

There were no serious adverse events (SAEs) including deaths or stopping rules met on study, no decrease of platelet count of 20% or more from baseline, and no clinically significant changes in platelet count (change of 5% from baseline combined with post-baseline result outside of normal ranges) that occurred during the study. No statistically significant differences were seen when comparing the changes in platelet count between baseline and post-infusion values for subjects in Thrombosomes and Control groups.

Although this study, and more specifically the individual treatment cohorts, contained a small number of subjects, which led to high variability in reported AEs, the frequency and nature of TEAEs reported in this study are consistent with AEs that are typically observed in a healthy volunteer population. Overall, no clinically significant abnormalities were reported after infusion of Thrombosomes, and the results were similar between the control and treated cohorts.

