### **1.16 Data Analysis**

Separate data summaries will be prepared for each cohort:

- Demographic and medical history data will be summarized. For quantitative variables, summaries will include the sample size, mean, median, standard deviation, minimum, and maximum. For qualitative variables summaries include the number and percent of patients for each outcome.
- Exploratory analyses will include the observed response and the change from baseline to each of the post-infusion time points for each of the laboratory tests (hematology, coagulation, platelet and chemistry). Additionally, summaries of the number and percent of patients with both a change of  $>5\%$  from baseline and whose results are outside of reference ranges will be displayed. For quantitative variables summaries of the observed response and the change from baseline to each of the post-baseline time points will include the sample size, mean, median, standard deviation, minimum, and maximum. Additionally, for the change from baseline summaries, the statistical significance will be determined using either a t-test or the Wilcoxon Signed Rank test, as appropriate. Summaries for qualitative variables will include the number and percent of patients for each outcome.
- Incidence of AEs and SAEs per patient and by body system will be summarized showing the number and percent of patients for each outcome. Summaries will also be prepared by severity and relationship to treatment.
- Summaries of vital signs and clinical data including WHO bleeding scores will include the observed response and the change from baseline to each of the post-infusion time points for each of the variables. For quantitative variables summaries of the observed response and the change from baseline to each of the post-baseline time points will include the sample size, mean, median, standard deviation, minimum, and maximum. Additionally, for the change from baseline summaries, the statistical significance will be determined using either a t-test or the Wilcoxon Signed Rank test, as appropriate. Summaries for qualitative variables will include the number and percent of patients for each outcome.

A statistical analysis plan will be developed as part of the data analysis plan.

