## 1 INTRODUCTION

This document outlines the methods of statistical analysis and data presentation associated with clinical study protocol (CSP) 2017-1, describing a Phase 1, multicenter, open-label, dose-escalation study. Within this study, the effects of escalating infusion doses of the investigational product, Thrombosomes®, will be assessed within a target population of actively-bleeding, thrombocytopenic patients (with platelet counts 5,000-70,000/ $\mu$ L). Patient inclusion will further be restricted to those with modified World Health Organization (WHO) bleeding severity scores of grade 1 (including only those patients with epistaxis, hematuria, oral petechiae, oropharyngeal bleeding, or bleeding at invasive or other wound sites) or grade 2, with bleeding due to hematologic/oncologic disease or bone marrow aplasia secondary to chemotherapy or radiotherapy. While the overall study design, study objectives and endpoints, and proposed methods for manipulating, analyzing, and presenting data are described below, the reader is referred to the CSP and case report forms for detailed descriptions of the investigational product, full list of patient inclusion/exclusion criteria, and data collection methods.

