## 9.1 Clinical Laboratory Assessments

Laboratory assessments to be used in efficacy analyses will include select hematology measures (hemoglobin, hematocrit, and platelets). Within a single table for each of 2 populations (Safety and Evaluable), the numbers and percentages of patients will be presented by categorized patterns of post-infusion change, including clinical improvement, stability/no change, and clinical worsening, for each of 2 post-infusion timeframes (infusion through the 24-hour post-infusion visit and infusion through the Day-6 visit). For each patient, categorization will require consideration of all measurements recorded across all time-points within the timeframe. For each hematology measure, clinical improvement and worsening will be defined as shown below. The category of stability/no change will apply by default when, for an individual patient, neither improved nor worsened conditions have been observed following infusion. When both improved conditions and worsened conditions have been distinctly observed at different time-points, the patient will fall into the category of clinical improvement.

Clinical improvement will be defined by:

- Hemoglobin increase of 1 g/dL
- Hematocrit increase of 3%
- Platelet count increase of 5,000/ $\mu$ L

Clinical worsening will be defined by:

- Hemoglobin decrease of 1 g/dL
- Hematocrit decrease of 3%
- Platelet count decrease of 5,000/ $\mu$ L

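### A flat 5,000/µL platelet threshold over an entry range of 5,000–70,000/µL gives uneven sensitivity, and scores large relative falls at low counts as stability

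*Protocol*

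**What the plan says.** **The rule.** SAP 9.1 (efficacy, clinical laboratory assessments) sorts each patient into improved, stable or worse on platelets. It does so over two windows: infusion to the 24-hour visit, and infusion to the Day-6 visit. All readings in the window are used. Improvement is a "Platelet count increase of 5,000"/µL and worsening is a "Platelet count decrease of 5,000"/µL. For the middle category: "The category of stability/no change will apply by default when, for an individual patient, neither improved nor worsened conditions have been observed following infusion". If both thresholds are met at different times, "the patient will fall into the category of clinical improvement".

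**The population.** The SAP Introduction describes "thrombocytopenic patients (with platelet counts 5,000-70,000" per µL. Protocol 1.11.1 sets the same limits.

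**The endpoint.** SAP 2.2.2 lists as a secondary endpoint the patients who show either stability or a change towards improvement in hematology measures. SAP 2.1.2 treats these patterns as early signals of efficacy.

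**Relative measures.** Protocol 1.6 reports for the earlier study "no decrease of platelet count of 20% or more from baseline". It also reports no clinically significant platelet change, meaning a "change of 5% from baseline combined with post-baseline result outside of normal ranges". For the present trial, Protocol 1.16 says that figures for patients who moved by more than 5% "from baseline and whose results are outside of reference ranges will be displayed". The SAP does not carry this over, and its section 11 list of main changes does not mention it. The change-from-baseline table in SAP 8.3 is limited to white cells and their differential, so platelets are left out.

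**The concern.** A fixed absolute change means very different things at the two ends of a fourteen-fold entry range. Near the floor a patient has almost no room to be classed as worse, while a rise of 5,000/µL is open to everyone, so the scale is one-sided where counts are lowest. Because stability is the default and is counted with improvement, a large relative fall in such a patient adds to the favourable side of a secondary efficacy endpoint. Thrombocytopenia is among the potential risks in Protocol Table 5, so this is a direction in which the display should be able to show harm.

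The dose comparison is also affected. Cohorts of 8 are filled in sequence, and SAP 6.5 plans no stratified or covariate-adjusted analysis. If baseline counts differ between cohorts by chance, the category rates will differ even when the relative change is the same.

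**Working it through.** The plan gives no calculation for this endpoint, so there is no figure to reproduce. The check applies the SAP 9.1 rule directly, reading *of 5,000* as *at least 5,000*.

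**Inputs.** Threshold T = 5,000/µL (SAP 9.1). Baseline B from 5,000 to 70,000/µL (SAP Introduction; Protocol 1.11.1).

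**Step 1: threshold as a share of baseline, T/B, for a patient with one post-infusion reading.**

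| B (/µL) | T/B | A halved count is | A 20% fall (/µL) is |
|---|---|---|---|
| 5,000 | 100% | stable | 1,000: stable |
| 8,000 | 62.5% | stable | 1,600: stable |
| 10,000 | 50% | worse | 2,000: stable |
| 20,000 | 25% | worse | 4,000: stable |
| 25,000 | 20% | worse | 5,000: worse |
| 50,000 | 10% | worse | 10,000: worse |
| 70,000 | 7.1% | worse | 14,000: worse |

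At 5,000 only a count of zero is worsening. A fall from 8,000 to 4,000 is a change of 4,000, hence stable.

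**Step 2: crossover points.** A fractional fall f is missed when f × B < T, that is when B < T/f. For f = 0.50 this is B < 10,000. For f = 0.20 it is B < 25,000. Below 25,000 the flat rule is laxer than a 20% fall; above it the flat rule is stricter.

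**Step 3: dependence on baseline mix.** Suppose every patient falls by 30%. At B = 12,000 the fall is 0.30 × 12,000 = 3,600, so all 8 of a cohort are stable. At B = 30,000 it is 0.30 × 30,000 = 9,000, so all 8 are worse. The relative effect is identical and the category rates are opposite.

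**Step 4: the upper end.** The documents give no count precision. As an assumption, take a coefficient of variation (CV) of 5% per count with no true change. The SD of a difference is B × 0.05 × √2, which is 4,950 at 70,000. One reading then crosses T in either direction with probability 31% at 70,000, about 16% at 50,000, about 2% at 30,000 and under 0.1% at 20,000. At an assumed 3% the SD at 70,000 is 2,970 and the probability is about 9%.

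**Step 5: how many patients.** This needs a baseline distribution, and none is given. Two assumed shapes on 5,000–70,000 show the spread:
- Uniform: (10 − 5)/65 = 8% of baselines lie below 10,000, and (25 − 5)/65 = 31% below 25,000.
- Log-uniform: ln 2/ln 14 = 26% and ln 5/ln 14 = 61%.

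These are shares of baselines in the zone where such falls would be missed. They are not rates of misclassified patients.

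**The case against.** The other side has several good points.

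- **No criterion was dropped.** A reader might infer from Protocol 1.6 that a 20% platelet criterion was abandoned. The documents do not support that. The 20% figure is a result reported for a study that Protocol 1.9.1 describes as done in healthy volunteers, and nothing makes it a rule for this trial. This stands.
- **Platelet falls are not hidden.** The SAP plans raw platelet summaries over time, abnormal-result and shift tables, per-patient plots by cohort and transfusion subgroup, graded adverse events and full listings. The Data Monitoring Committee also receives selected hematology listings. With 24 planned patients, a fall from 8,000 to 4,000 can be found. This stands. However, the plots and listings do not count patients by size of fall, and a shift table shows nothing new if the value was already in its worst category at baseline.
- **A halved low count is not always called stable.** All readings count and improvement takes precedence. Protocol 1.9.2.2 restricts platelet transfusion from six hours before to one hour after infusion, and lets physicians transfuse at any time for unchanged or worsening bleeding. A patient with a low count who is transfused may be classed as improved. This stands and limits the claim. It also means that a fall can vanish behind a later rise.
- **Absolute or relative change is a matter of judgement.** The flat rule is the stricter one above 25,000/µL, so it is not lax throughout. This stands, and is why the flat rows should stay.
- **Little rides on the table.** It is descriptive, has no planned between-cohort test, and triggers no stopping or dose decision. This stands.

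**Conclusion.** The point holds as one of uneven sensitivity. The worsening threshold runs from 100% of baseline at 5,000/µL to 7% at 70,000/µL. A halved count from any baseline below 10,000 is stability, provided that no reading in the window rises by 5,000 or more. A 20% fall from any baseline below 25,000 is also stability, provided that no other reading moves by 5,000 in either direction. Because stability is counted with improvement, these falls are scored as favourable, and cohort rates shift with the baseline mix.

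These results follow from the SAP's own rule; they assume only that the threshold means at least 5,000/µL. The share of patients affected cannot be stated, and the noise probabilities at high counts rest on an assumed CV. The weakness lies in one descriptive secondary display and does not threaten the trial's safety monitoring. Two omissions make it more worth repairing: platelets are absent from the change-from-baseline table, and the relative summary in Protocol 1.16 has no counterpart in the SAP.

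**What to change.** In SAP 9.1 and Tables 14.2.1.1 and 14.2.1.2, keep the 5,000/µL rows exactly as defined. Beside them add separate platelet rows, by cohort and overall and for each of the two windows, giving the number and percentage of patients with:

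- a fall from baseline of 20% or more at any reading in the window;
- a fall from baseline of 50% or more at any reading in the window.

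Count these patients whether or not they also rose by 5,000/µL at another time, so that a later rise cannot mask a fall. State that the stability rows are to be read beside the new ones. Do not bar patients from the stable category on a relative criterion, since that would redefine the retained rows.

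Also add platelets to the hematology change-from-baseline table (Table 14.3.5.2).

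The cost is a few rows of programming on data already collected, with no change to trial conduct. The small downside is that a 20% change at very low counts is only about 1,000/µL at a baseline of 5,000 and may be noisy. That is why the absolute and 50% rows are shown alongside it.

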## 1.7 Product Information & Indications for Use

Thrombosomes are a lyophilized product prepared from a pool of group O human platelets (collected from 5-10 donors) that are being developed for the treatment of uncontrolled hemorrhage. Each vial from each lot of Thrombosomes contains a mean of 1.7 x 10^9 Thrombosomes particles per ml and an associated activity of approximately 3400 TGPU per ml after rehydration with 10 ml of sterile water for injection. Based upon efficacy studies in a thrombocytopenic New Zealand White Rabbit (NZWR) ear bleed model, the lowest observed efficacious dose was (1.89 x 10^8 particles per kg or 330 TGPU per kg). Refer to the *Investigator's Brochure* for additional information.

---

 National Highway Traffic Safety Administration Fatality Analysis Reporting System (FARS) 1975-2009 – <http://nhtsa.gov/FARS>

## 1.8 Objectives

The primary and secondary objectives of this trial, conducted in thrombocytopenic patients (platelet count  $\geq$  5,000/  $\mu$ L and  $\leq$  70,000/ $\mu$ L) with modified World Health Organization (WHO) Grade 1\* or 2 bleeding are:

### 1.8.1 Primary

- Assess the safety of infusing increasing doses (approximately 5 ml, 10 ml, and 20 ml) of allogeneic Thrombosomes which are equivalent to approximately  $9.45 \times 10^7$  particles/kg or 165 TGPU per kg,  $1.89 \times 10^8$  particles/kg or 330 TGPU per kg and  $3.78 \times 10^8$  particles/kg or 660 TGPU per kg, respectively.

### 1.8.2 Secondary

- Assess the effect, on WHO bleeding score, of increasing doses of allogeneic Thrombosomes.
- Assess the effect of increasing doses of allogeneic Thrombosomes on measures of coagulation.

\* Note: Only a subset of patients with Grade 1 bleeding who have either epistaxis, hematuria, oral petechiae, oropharyngeal bleeding, or bleeding at invasive or other wound sites.

## 1.9 Study Design

### 1.9.1 Introduction

This study will require enrollment of patients into three cohorts in order to evaluate, in a dose-escalation manner, the safety, and preliminary impact on bleeding, and the preliminary effect on coagulation measures of increasing doses of allogeneic Thrombosomes. Data from this study will provide information on the safety, and possibly potency of three increasing doses of Thrombosomes in order to support the design of future clinical protocols in bleeding patients. The proposed starting dose in this protocol is approximately five (5) times the highest dose used in a previous dose escalation study in normal healthy volunteers. For further information regarding minimum effective dose, maximum feasible dose and safety margins from previous clinical and non-clinical investigations, see the Investigator's Brochure.

### 1.9.2 Methodology

This is a Phase 1, multicenter, open-label, dose-escalation study in hospitalized, bleeding, and thrombocytopenic patients. Patients with modified WHO Grade 1 (see note following Table 1. Cohort Assignment) or Grade 2 bleeding due to hematology/oncology diseases or bone marrow aplasia secondary to cancer chemo/radiotherapy will be enrolled on study and treated with allogeneic Thrombosomes (See

Appendix A- Modified WHO Bleeding Score). Patients with WHO Grade 0, 3, or 4 bleeding do not meet eligibility criteria for enrollment. The protocol will require three cohorts of patients consisting of 8 patients in each cohort for a total of 24 patients (See Table 1. Cohort Assignment).

Table 1. Cohort Assignment				
Cohort	1	2	3	Total
	n	n	n	n
WHO Grade 1*or 2	8	8	8	24

Note: \*Only a subset of patients with Grade 1 bleeding who have either epistaxis, hematuria, oral petechiae, oropharyngeal bleeding, or bleeding at invasive or other wound sites.

